6.3.1.2.7 Unsolicited Adverse Events

Unsolicited AEs are defined as any spontaneously reported or discovered AE.

Unsolicited AEs will be collected in all participants who receive at least 1 dose of the study vaccine and are classified according to the following:

- Mild, moderate, or severe
- Whether or not the AE was categorized as an SAE, an MAAE, and/or an AE leading to discontinuation of the study vaccine/ study withdrawal
- Whether or not the AE was related to the study vaccine or the study procedure in the judgment of the Investigator

6.3.1.2.8 Eliciting and Documenting Adverse Events

AEs will be assessed from the time the participant signs the informed consent form (ICF) until exit from the study. Safety follow-up will be continued for 12 months after last injection of the study vaccine (up to last study visit). Any ongoing AE that a participant is experiencing at the time of Screening (e.g., intercurrent illness) should be captured as medical history.

Solicited AEs will be solicited by Paper Diary for 7 days after each study vaccination in all participants.

At every clinic visit and daily (for 7 days after each vaccination) by Paper Diary, participants will also be asked a standard nonleading question to elicit any medically related changes in their well-being. Any and all new changes to the participant's health (including exacerbation of underlying disease) that are not solicited events will be regarded as an unsolicited AE.

In addition to participant observations, AEs identified from any study data (e.g., clinically significant findings or changes on physical examination, safety laboratory assessments, VS) or identified from review of other documents (e.g., participant Paper Diary) that are relevant to participant safety will be documented on the AE page on the eCRF.

All unsolicited AEs will be collected for 28 days after each study vaccination. Unsolicited AEs that meet the protocol definition of MAAE, SAE, or AEs leading to discontinuation of the study vaccine/study withdrawal will be captured for the duration of study participation.

If the Investigator learns of any SAE, including a death, at any time after a participant has been discharged from the study, and he/she considers the event to be reasonably related to the study vaccine or study participation, the Investigator must promptly notify the Sponsor.

Solicited and unsolicited AEs will be coded by System Organ Class (SOC) and Preferred Term (PT) according to the Medical Dictionary for Regulatory Activities (MedDRATM). Note: Injection site tenderness will be coded only to the lower-level term, as there is no PT of injection site tenderness (it codes to a PT of injection site pain).

6.3.1.2.9 Assessment of Severity

Solicited AEs: The intensity of solicited AEs will be graded for severity as Grade 0, Grade 1 (mild), Grade 2 (moderate), Grade 3 (severe), or Grade 4 (potentially life threatening). The severity of solicited AEs will be assessed according to scales based on the US FDA toxicity grading scales for vaccine clinical studies, as shown in [Appendix 5](#).

Unsolicited AEs: The severity of unsolicited AE will be rated as mild, moderate, or severe using the following criteria:

Mild:

- These events require minimal or no treatment and do not interfere with the participant's daily activities.

OR

- An event usually transient in nature and generally not interfering with normal activities.

Moderate:

- These events result in a low level of inconvenience or concern with the therapeutic measures. Moderate events may cause some interference with normal functioning.

OR

- An AE that is sufficiently discomforting to interfere with normal activities.

Severe:

- These events interrupt a participant's usual daily activities and may require systemic drug therapy or other treatment. Severe events are usually incapacitating.

OR

- An AE that is incapacitating and prevents normal activities.

6.3.1.2.10 Assessment of Causality

Solicited AEs: These are, by definition, regarded as related to the study vaccine. Therefore, causality is not assessed.

Unsolicited AEs: The Investigator's assessment of an unsolicited AE's relationship to the study vaccine is part of the documentation process, but it is not a factor in determining what is or is not reported in the study. If there is any doubt as to whether a clinical observation is an AE, the event should be reported.

The relationship or association of the study vaccine in causing or contributing to the AE will be characterized using the following classification and criteria:

- Unrelated: There is no association between the study vaccine and the reported event.
- Possible: Treatment with the study vaccine caused or contributed to the AE, i.e., the event follows a reasonable temporal sequence from the time of study vaccine administration or follows a known response pattern to the study vaccine but could also have been produced by other factors.
- Probable: A reasonable temporal sequence of the event with study vaccine administration exists and, based upon the known pharmacological action of the drug, known or previously reported adverse reactions to the drug or class of drugs, or judgment based on the Investigator's clinical experience, the association of the event with the study vaccine seems likely. The event disappears or decreases on cessation or reduction of the dose of the study vaccine.
- Definite: A definite causal relationship exists between study vaccine administration and the AE, and other conditions (concurrent illness, progression/expression of disease state, or concurrent medication reaction) do not appear to explain the event. The event reappears or worsens if the study vaccine is readministered.

In addition to the Investigator's assessment of relatedness, the Sponsor or designee will evaluate the available information and perform an independent assessment of all reported SAEs and determine if there is a reasonable possibility that the study vaccine is causally related to a reported SAE.

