
	intended for administration to individuals who may or may not have been previously vaccinated.
Target Population	Adult participants ≥ 21 to ≤ 65 years of age will initially be enrolled in one or more of the following countries – Singapore, South Africa or the US. Cohort A participants will not have previously received SARS-CoV-2 vaccinations while participants in Cohort B will have previously received 2 doses of the BNT162b2 SARS-CoV-2 vaccine 5 months or longer prior to study enrollment.
Number of Participants	Approximately 72 adults ≥ 21 to ≤ 65 years of age (up to a maximum of 144 adults ≥ 21 to ≤ 80 years if additional cohorts are added) will be enrolled. Cohort A will include approximately 36 SARS-CoV-2 vaccine-naïve adults. Within Cohort A, Sub-cohort A1 will include 12 participants who are seronegative at screening and Sub-cohort A2 will include 24 participants who are seropositive at screening. Cohort B will include approximately 36 SARS-CoV-2-vaccinated adults.
Length of Participation	Cohort A participants - Screening period of up to 28 days and Vaccination Visit through Final Visit of up to 394 days; a total of up to 422 days Cohort B participants - Screening period of up to 28 days and Vaccination Visit through Final Visit to 366 days; a total of up to 394 days
Intervention	The study will evaluate 3 investigational vaccines: 
 • ARCT-021: A self-amplifying RNA vaccine coding for wild-type ancestral strain spike antigen • ARCT-154: A self-amplifying RNA vaccine coding for the D614G variant of ancestral strain spike antigen • ARCT-165: A self-amplifying RNA vaccine coding for the SARS-CoV-2 Beta variant of SARS-CoV-2 and also containing the D614G variant mutation • All 3 investigational vaccines will be administered as a 5-μg dose in 0.5-mL volume administered intramuscularly into the deltoid muscle. If additional cohorts are added, the dose of each study vaccine will not exceed 5 μg at each injection. • Participants will receive 1 or 2 doses based on cohort assignment. • Cohort A participants will receive 2 doses (28 days apart) of ARCT-165, ARCT-154, or ARCT-021. • Cohort B participants will receive 1 dose of ARCT-165, ARCT-154, or ARCT-021.

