4.2.2 Discontinuation of Study Vaccine (Participant)

4.2.2.1 Stopping Rules for Adverse Events in Individual Participants

A participant must not receive further study vaccine administrations if they experience any of the following AEs:

- Grade 3 solicited AEs (as confirmed by a blinded SRC review)
- Any anaphylactic reaction
- Severe related (possibly, probably, or definitely) unsolicited AEs
- Any clinically apparent hypersensitivity episode that is considered at least moderate in severity, is considered possibly, probably, or definitely related to study vaccine administration (as assessed by the Investigator and review of the SRC) and has the following features:
 - is not confined to the injection site
 - is immediate in onset (within ≤ 4 hours after vaccination) OR if delayed, involves more than one organ system
- Any serious adverse event (SAE) judged to be related (possibly, probably, or definitely) to study vaccine.
- Myocarditis and/or pericarditis
- Hypertensive crisis

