4.2.4 Study-Wide Pausing and Stopping Rules

If any of the following is observed in the study, further administration of study vaccine to all participants will be paused until the blinded SRC has reviewed all relevant safety data and determined that it is safe for dosing with study vaccine to resume. Termination of the study will depend on evaluation of these safety data and the findings of the SRC.

- Any SAE considered possibly, probably, or definitely related to study vaccine administration (as confirmed by SRC review)
- Any anaphylactic AE following study vaccine administration

- Any clinically apparent hypersensitivity episode that is considered at least moderate in severity, is considered probably or definitely related to study vaccine administration (as confirmed by SRC review), and has the following features:
 - Is not confined to the injection site
 - Is immediate in onset (within ≤ 4 hours after vaccination) or, if delayed, involves more than 1 organ system
- Any suspected or confirmed myocarditis, pericarditis, and/or myopericarditis event that is considered by the investigator to be possibly, probably, or definitely related to study vaccine administration or is temporally associated (within 6 weeks) with vaccine administration.
- Any death due to SARS-CoV-2 infection or any severe (per the Food and Drug Administration [FDA] criteria [[Appendix 7](#)]) SARS-CoV-2 infection in a vaccinated participant.

Events meeting Pausing Rule definitions will be referred to the SRC (which will remain blinded to the vaccine assignment), where the case details and the assessment of the event causality will be assessed. Should the SRC confirm that a Pausing Rule was met, Investigators will be immediately instructed to pause dosing, and the applicable health authorities will be notified within 1 business day of determination that a Pausing Rule has been met.

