5.8 Dose Modification

No dose modifications will be allowed.

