- Participant incidence of unsolicited AEs post each vaccination through end of study by relationship to study vaccine, MedDRA system organ class and preferred term;
- Participant incidence of unsolicited AEs post each vaccination through end of study by relationship to study procedure, MedDRA system organ class and preferred term;
- Overall summary of unique MAAEs post each vaccination and participant incidence of AEs meeting various criteria, including (but not limited to), AESIs, AEs leading to discontinuation, SAEs, and deaths;
- Participant incidence of MAAEs post each vaccination by system organ class, and preferred term;
- Participant incidence of related MAAEs post each vaccination by system organ class and preferred term;
- Participant incidence of SAEs post each vaccination by system organ class, and preferred term;
- Participant incidence of SAEs post each vaccination by relationship to study vaccination, system organ class, and preferred term;
- Participant incidence of SAEs post each vaccination by relationship to study procedure, system organ class, and preferred term;
- Participant incidence of AESIs post each vaccination by system organ class and preferred term; and
- Participant incidence of AEs leading to discontinuation/withdrawal post each vaccination by system organ class and preferred term; and
- Participant incidence of AEs leading to death post each vaccination by system organ class and preferred term.

At each level of summarization (e.g., any AE, system organ class, and preferred term), participants experiencing more than one AE will be counted only once. In the summary of AEs by toxicity or severity grade, participants will be counted once at the highest toxicity or severity reported at each level of summarization; in the summary of unsolicited AEs by relationship, participants will be counted once at the closest relationship to study vaccine or procedure. Related events include those relationship to study vaccine or procedure is reported as “Possible,” “Probable,” or “Definite;” events considered not related are those reported as “Unrelated” to study vaccine or procedure. The total number of patients reporting events in each individual relationship category will also be summarized, in addition to the “Related” and “Unrelated” categories.

Adverse event data will be presented in data listings by sub-cohort (Cohort A only), participant, study vaccine group, and event.

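### The causality scale in Protocol 6.3.1.2.10 ends Probable and Definite with dechallenge and rechallenge sentences that do not fit a fixed one- or two-injection vaccine, so ratings may be assigned inconsistently

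*Protocol*

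**What the plan says.** Protocol 6.3.1.2.10 has investigators rate each unsolicited AE as Unrelated, Possible, Probable or Definite.

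- **Possible** covers plausible timing or a known response pattern, with the proviso that the event "but could also have been produced by other factors".
- **Probable** asks for reasonable timing and a likely association, then adds "The event disappears or decreases on cessation or reduction of the dose of the study vaccine".
- **Definite** asks for a definite causal link with no other apparent explanation, then adds "The event reappears or worsens if the study vaccine is readministered".

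The regimen is fixed. Section 5.8 states "No dose modifications will be allowed". The synopsis states "Cohort B participants will receive 1 dose of ARCT-165, ARCT-154, or ARCT-021", and Cohort A receives two doses, on Days 1 and 29. Section 4.2.2.1 opens "A participant must not receive further study vaccine administrations if they experience any of the following AEs". Its list includes anaphylaxis, related SAEs, severe related unsolicited AEs, and related systemic hypersensitivity of moderate or greater severity. For the last three, a rating of Possible is enough.

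The ratings are used in two places. Unsolicited AEs by relationship are part of primary Endpoint 1. SAP 4.6.2 pools Possible, Probable and Definite as related and adds "The total number of patients reporting events in each individual relationship category will also be summarized". Separately, the study-wide hypersensitivity pause in Protocol 4.2.4 counts an episode only if it "is considered probably or definitely related to study vaccine administration (as confirmed by SRC review".

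**The concern.** The two closing sentences come from a scale for a drug given repeatedly, where treatment can be stopped, reduced or restarted. Here each dose is one injection, so there is no course to stop in the usual sense, no dose to reduce and often no second injection.

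If the sentences are taken as requirements, an investigator convinced that the vaccine caused an event may find neither of the two higher categories formally open. Possible fits poorly too, because it presupposes that other factors could explain the event. Another investigator may treat the same sentences as satisfied or irrelevant. The SAP expects about 4 sites (4.8.1.4) and gives no rule to make the readings agree.

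Two things are at stake: whether the category-level relationship counts can be interpreted, and whether a systemic hypersensitivity episode that is neither anaphylactic nor serious meets the pausing criterion. The sponsor's independent causality assessment in 6.3.1.2.10 covers SAEs only, so it would not reach that episode.

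**Working it through.** The plan gives no figure to reproduce. The check is a count of planned injections, followed by a comparison of the sections.

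**Inputs (Protocol 3.1 and 5.8).** Cohort A: 36 participants (A1 12, A2 24), two injections each. Cohort B: 36 participants, one injection each. No dose modification.

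**Step 1: planned injections.** 36 × 2 + 36 × 1 = 108, in 36 + 36 = 72 participants.

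**Step 2: dose reduction possible.** 0 of 108.

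**Step 3: readministration possible.** Only Cohort A first injections are followed by another: 36/108 = 33.3% of injections, in 36/72 = 50% of participants. The other 108 − 36 = 72 injections (72/108 = 66.7%) are not. The 33.3% is an upper bound, because 4.2.2.1 removes some second doses.

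**Step 4: what remains in Cohort A.** A dose 1 event on the 4.2.2.1 list cannot be rechallenged. A dose 1 event that does not bar dose 2 can recur or worsen after Day 29, and then the Definite sentence can be met.

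**Step 5: the possible readings.**

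| Sentence | Taken as a requirement | Taken loosely or conditionally |
|---|---|---|
| Probable: improvement on cessation or reduction | Reduction never occurs; an injection already given cannot be stopped, so unmeetable | Any transient event that resolves with no further dosing qualifies, so it does not discriminate |
| Definite: recurrence on readministration | Unmeetable in Cohort B, after dose 2, and after a barring dose 1 event | Not applicable where no further dose is given; the category rests on its first sentence |

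Take a Cohort B event with good timing, a known reaction pattern and no other explanation. On the strict reading it fails Definite and Probable and is left with a poorly fitting Possible. On the conditional reading it is Definite.

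**Step 6: effect on the SAP tables.** A shift among Possible, Probable and Definite leaves the pooled related count unchanged. The counts by individual category do change.

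**Step 7: effect on the 4.2.4 pausing criteria.**

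- Anaphylaxis: no causality category needed.
- SAE: Possible is enough.
- Myocarditis or pericarditis: Possible, or timing alone, is enough.
- Fatal or severe SARS-CoV-2 infection: no causality category needed.
- Hypersensitivity: Probable or Definite needed.

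Only the last depends on the disputed boundary.

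**Step 8: arms.** Group sizes are A1 12/3 = 4 per vaccine, A2 18 and 6, and B 36/3 = 12 per vaccine. Across the study, the share of participants with two planned doses would be 4/16 (25.0%) for ARCT-165, 22/34 (64.7%) for ARCT-154 and 10/22 (45.5%) for ARCT-021. SAP 4.1.1 reports the cohorts separately, and Cohort A by sub-cohort. Within each of these, every arm has the same number of doses, so the regimen creates no difference between arms in the planned tables.

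**The case against.** A reader might infer that Probable and Definite are largely unreachable in this trial. The text does not support that. The Definite sentence contains the word *if* and can be read as silent where no second dose is given. The Probable sentence offers cessation as an alternative to reduction, so section 5.8 closes only one route. A Cohort A event that does not bar dose 2 can be rechallenged in fact. These points stand, and they limit the finding to ambiguity.

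The safety consequence also has safeguards. Under 7.6.1 the SRC reviews all AEs that potentially meet a pausing rule, 4.2.4 has it assess causality of referred events, and 4.2.2.1 brings the hypersensitivity episode to it at Possible. A rating of Possible therefore need not keep the episode from the SRC. This is a real mitigation but not a complete one. No other causality scale is given for the SRC, and the 4.2.2.1 route has practical effect only while a further dose is pending.

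The different relatedness thresholds in 4.2.2.1 and 4.2.4 may be deliberate, since one stops an individual's dosing and the other pauses the study. The difference alone is not an error, but the documents do not say that it is intended.

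Finally, the analyses are descriptive, and solicited reactions are treated as related by definition and never rated on this scale. Both points are correct and keep the reporting impact small.

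**Conclusion.** The point holds in a limited form. The two sentences do not fit the regimen: dose reduction is possible for 0 of 108 planned injections, and at least 72 of 108 have no planned readministration. Depending on the reading, the sentences are unmeetable, trivially met or not applicable, so ratings within the related categories may be inconsistent.

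The reach is narrow: the counts by individual relationship category, and one pausing criterion that SRC review partly protects. The pooled related/unrelated summary and the other pausing criteria are unaffected. Nothing here shows that the primary safety endpoint as a whole is compromised or that one arm is favoured.

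The conclusion assumes the planned cohort sizes and full dosing. It also assumes that investigators could reasonably differ in their reading; the documents do not show that they have.

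**What to change.** In Protocol 6.3.1.2.10, either remove the last sentence of Probable and of Definite, or qualify each as applying only where dechallenge or readministration actually occurs. The categories would then rest on the timing, known-reaction and alternative-explanation criteria already written there.

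Then reconcile the hypersensitivity relatedness wording in 4.2.2.1 and 4.2.4 with the revised scale and with each other, or state that the difference is intended. Which threshold applies is a clinical decision on which this review takes no view. Those responsible for safety should make it knowingly, because changing the scale may change which episodes meet the 4.2.4 criterion.

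The cost is a short amendment and a site memo, with no new assessments. The downside is that AEs already rated may need a query so that one scale applies throughout. That includes Cohort B, for which Protocol 3.1.1 already cites preliminary data.

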6.3.1.2.11 Reporting Adverse Events

The recording of non-serious AEs will begin after the participant has signed the informed consent form (ICF) and will stop at the end of the participant's follow-up period, which is defined as the participant's last protocol-specified study visit. The Investigator will monitor each participant closely and record all observed or volunteered AEs in the electronic data capture (EDC) system.

AEs that occur prior to administration of the study vaccine will be recorded as medical history.

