Primary Objectives and Primary Endpoints	
Objective 1: To describe the safety and reactogenicity of 3 investigational SARS-CoV-2 self-amplifying RNA vaccines
 
Endpoint 1: Safety will be summarized for each vaccination as the number and percentage of participants with the following:
 
 a. Any solicited local or systemic adverse event (AE) collected for 7 days after each study vaccination, which will be assessed by toxicity grade b. Any unsolicited AE collected for 28 days after each study vaccination, which will be assessed by severity and relationship to study vaccine c. Any medically attended adverse events (MAAEs), AEs leading to discontinuation from study vaccine/study withdrawal, or serious

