6.3.1 Adverse Events

6.3.1.1 Definitions

6.3.1.2 Adverse Events

The Investigator is responsible for reporting all AEs that are observed or reported during the study, regardless of their relationship to the study vaccine or their clinical significance. AE collection will begin after the signing of informed consent; however, AEs that occur prior to the administration of first dose of the study vaccine (i.e., non-treatment-emergent AEs) will be listed separately in the CSR.

An AE is defined as any untoward medical occurrence associated with the use of a medicinal product in humans, whether or not considered related to the medicinal product.

An AE, therefore, can be any of the following:

- Any unfavorable and unintended sign (including an abnormal laboratory finding), symptom, or disease temporally associated with the use of a medicinal product, whether or not considered related to the medicinal product

- Any new disease or exacerbation of an existing disease (a worsening in the character, frequency, or severity of a known condition)
- Recurrence of an intermittent medical condition (e.g., headache) not present at baseline
- Any deterioration in a laboratory value or other clinical test (e.g., electrocardiogram [ECG], X-ray) that is associated with symptoms or leads to a change in study treatment or concomitant treatment or discontinuation from the study vaccine
- AEs that are related to a protocol-mandated intervention, including those that occur prior to administration of the study vaccine (e.g., Screening invasive procedures such as biopsies)

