3.4.2.1 Adverse Events

An AE is defined as any untoward medical occurrence associated with the use of a medicinal product in humans, whether or not considered related to the medicinal product. Adverse event collection will begin after the signing of informed consent and continue through study exit. Adverse events that occur prior to the administration of first dose of the study vaccine (i.e., non-study vaccine-emergent AEs) will be listed separately in the CSR.

An adverse event of special interest (AESI), including both serious and non-serious events, include myocarditis, pericarditis, and myopericarditis.

Adverse events will be collected on two distinct CRFs to capture solicited AEs and unsolicited AEs.

Solicited AEs refer to selected signs and symptoms occurring in the hours and days following a vaccination. These will be collected from participants on paper diary cards for seven consecutive days following each study vaccine administration. The following solicited AEs are included in the paper diary:

- Solicited local AEs: Injection site erythema, injection site pain, injection site induration/swelling, and injection site tenderness
- Solicited systemic AEs: Arthralgia, chills, diarrhea, dizziness, fatigue, fever (categorized by measured body temperature), headache, myalgia, and nausea/vomiting

The occurrence of each of these solicited AEs is regarded as vaccine-related AE. Solicited AEs are graded for severity according to the 5-point scales defined in the US FDA's Center for Biologics Evaluation and Research's Guidance: *Toxicity Grading Scale for Healthy Adult and Adolescent Volunteers Enrolled in Preventive Vaccine Clinical Trials* (2007).

Unsolicited AEs are defined as any spontaneously reported or discovered AE. Unsolicited AEs will be collected in all participants who receive at least one dose of the study vaccine and are classified according to the following:

- Mild, moderate, or severe;
- Whether or not the AE was categorized as an SAE, a MAAE, and/or an AE leading to discontinuation of the study vaccine/ study withdrawal; and
- Whether or not the AE was related to the study vaccine or the study procedure in the judgment of the Investigator.

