The number of participants reporting SAEs, MAAEs, AESIs, AEs leading to discontinuation/withdrawal of vaccination, or AEs leading to death will also be presented.

Summaries of unsolicited AEs that are displayed by system organ class and preferred terms will be ordered by descending incidence of system organ class and preferred term within each system organ class for the 154-01 study vaccine group. Summaries displayed by preferred term only will be ordered by descending incidence of preferred term for the 154-01 study vaccine group.

Summaries of the following types will be presented:

- Summary of solicited AEs within 7 days post each vaccination
- Summary of solicited AEs within 7 days post each vaccination by toxicity grade and day
- Summary of solicited AEs within 7 days post each vaccination by toxicity grade
- Summary of duration (days) of solicited AEs post each vaccination
- Overall summary of unique unsolicited AEs and participant incidence of AEs meeting various criteria, including (but not limited to), AESIs, AEs leading to discontinuation, SAEs, and deaths, within 28 days of each vaccine administration;
- Most frequently-occurring ($\geq 10\%$ Overall) unsolicited AEs within 28 days of each vaccination by preferred term
- Participant incidence of unsolicited AEs up to 28 days post each vaccination by MedDRA system organ class and preferred term;
- Participant incidence of unsolicited AEs up to 28 days post each vaccination by severity, MedDRA system organ class, and preferred term;
- Participant incidence of unsolicited AEs up to 28 days post each vaccination by relationship to study vaccine, MedDRA system organ class, and preferred term;
- Participant incidence of unsolicited AEs up to 28 days post each vaccination by relationship to study procedure, MedDRA system organ class, and preferred term;
- Overall summary of unique unsolicited AEs and participant incidence of AEs meeting various criteria, including (but not limited to), AESIs, MAAEs, AEs leading to discontinuation, SAEs, and deaths through end of study;
- Most frequently-occurring ($\geq 10\%$ Overall) unsolicited AEs through end of study by preferred term
- Participant incidence of unsolicited AEs post each vaccination through end of study by MedDRA system organ class and preferred term;

- Participant incidence of unsolicited AEs post each vaccination through end of study by severity, MedDRA system organ class and preferred term;

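### Protocol 6.3.1.2.11 conflicts with the 28-day AE window and the pre-dose AE rule; if the 28-day window operates, the SAP's end-of-study unsolicited AE tables are not incidences over follow-up

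*Protocol*

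**What the plan says.** **When recording stops.** Protocol 6.3.1.2.11 starts recording of non-serious AEs at consent and says it "will stop at the end of the participant's follow-up period, which is defined as the participant's last protocol-specified study visit". It tells the investigator to enter every AE seen or reported, with no limit by event type.

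Protocol 6.3.1.2.8 says "All unsolicited AEs will be collected for 28 days after each study vaccination". After that, "Unsolicited AEs that meet the protocol definition of MAAE, SAE, or AEs leading to discontinuation of the study vaccine/study withdrawal will be captured" until participation ends. Primary endpoint 1b (Synopsis and Table 2) uses the same window: "Any unsolicited AE collected for 28 days after each study vaccination, which will be assessed by severity and relationship to study vaccine". Endpoint 1c, which runs to the Final or Early Termination Visit, covers only MAAEs, SAEs and AEs leading to discontinuation or withdrawal. Footnote p in Appendices 1 and 2 repeats the 28-day window and adds AEs associated with an unscheduled visit.

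**Events before the first dose.** Protocol 6.3.1.2 collects AEs from consent and says that pre-dose ones "will be listed separately in the CSR"; SAP 3.4.2.1 agrees. Protocol 6.3.1.2.11 ends with the opposite instruction: "AEs that occur prior to administration of the study vaccine will be recorded as medical history".

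**What the SAP tabulates.** SAP 4.6.2 reports unsolicited AEs over the 28-day windows and again to end of study. The second set includes "Participant incidence of unsolicited AEs post each vaccination through end of study by MedDRA system organ class and preferred term". It also has an overall summary, a list of terms at 10% or more, and tables by severity, relationship to vaccine and relationship to procedure. None of these six is limited to the event types still collected after 28 days. SAP 4.10 declares no change from the protocol's planned analyses.

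**The concern.** AE interviews continue at every late visit (Days 119, 209, 299 and 394 in Cohort A; Days 91, 181, 271 and 366 in Cohort B). A mild AE that needed no care and is first mentioned at Day 209 must be entered under 6.3.1.2.11, but no instruction in 6.3.1.2.8 asks for it. A new event between consent and first dose is an AE in one section and medical history in another.

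Describing safety is a primary objective, so the AE percentages are themselves the result. If late events enter a table only because they were serious, medically attended or led to discontinuation, a column labelled as running to end of study understates incidence by an unknown amount. It also shifts the severity and relationship mix towards events that met a capture criterion. The content of the pre-dose listing would depend on which section a site followed.

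**Working it through.** **1. Stop point, sections side by side.** For a non-serious unsolicited AE more than 28 days after a dose that is not medically attended, not tied to an unscheduled visit and not a cause of discontinuation or withdrawal:

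- Protocol 6.3.1.2.11: record it.
- Protocol 6.3.1.2.8, endpoint 1b, footnote p (both cohorts): outside the collection window.
- SAP 3.4.2.1, "Adverse event collection will begin after the signing of informed consent and continue through study exit": silent. The sentence gives only the outer limits of collection. Protocol 6.3.1.2.8 opens the same way, assessing AEs from consent to study exit, before setting windows by event type.

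The stop-point conflict therefore rests on 6.3.1.2.11 alone.

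**2. Pre-dose events.** Protocol 6.3.1.2 and SAP 3.4.2.1 treat them as AEs for a separate listing, and footnote p collects unsolicited AEs from Screening. Protocol 6.3.1.2.11 sends them to medical history, although its own first sentence starts AE recording at consent. The medical-history rule in 6.3.1.2.8 covers only conditions already ongoing at Screening, so it does not settle the matter.

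**3. Length of follow-up.** The Final Visit is 365 days after the last dose. Cohort A: 29 + 365 = Day 394. Cohort B: 1 + 365 = Day 366. Both match the schedules. From first dose to Final Visit is 394 − 1 = 393 days and 366 − 1 = 365 days.

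**4. Share with full capture under the 28-day rule** = (28 × doses) / (days from first dose to Final Visit), with doses on schedule.

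- Cohort A: 56 / 393 = 14.2%, leaving 85.8% under selective capture.
- Cohort B: 28 / 365 = 7.7%, leaving 92.3%.

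Under 6.3.1.2.11 both shares would be 100%.

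**5. Illustration on assumed rates.** The documents give no AE rate. Assume a constant rate λ of unsolicited AEs per person-year, with a fraction m of late events qualifying for capture. With F = λ × full days / 365.25 and R = λ × remaining days / 365.25, the expected share of participants with any unsolicited AE is 1 − exp(−(F + mR)) under the 28-day rule and 1 − exp(−(F + R)) under full capture.

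| Cohort | λ | 28-day rule, m = 0.2 to 0.5 | Full capture |
|---|---|---|---|
| A | 0.5 | 15.5% to 26.5% | 41.6% |
| A | 1 | 28.7% to 45.9% | 65.9% |
| A | 2 | 49.1% to 70.8% | 88.4% |
| B | 0.5 | 12.2% to 23.6% | 39.3% |
| B | 1 | 23.0% to 41.6% | 63.2% |
| B | 2 | 40.7% to 65.9% | 86.4% |

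These values show only that the rule followed could move the table totals substantially.

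**6. The list of terms at 10% or more.** In Cohort B (36 participants), 3/36 = 8.3% and 4/36 = 11.1%. One late event recorded or not can decide whether a term is listed.

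**The case against.** The strongest reply is that the operative rule is clear. Endpoints 1b and 1c, section 6.3.1.2.8 and both schedules agree, and one loosely worded section does not displace them. A site that records everything to the last visit also satisfies the 28-day minimum, so on the stop point the two texts are not strictly incompatible in practice. This stands as a reason to expect the 28-day rule to operate. It does not help the SAP tables, because that is the case in which their late content is selective.

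The selection is also milder than it may seem. An MAAE is any AE leading to an unscheduled contact with a health care provider, telemedicine included, with no severity threshold, and footnote p keeps AEs tied to unscheduled visits. That limits the distortion of the severity mix but does not remove it.

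Finally, SAP 4.6.2 has separate 28-day unsolicited tables and separate MAAE, SAE, AESI, discontinuation and death tables. Endpoints 1b and 1c can be reported cleanly. This stands in full.

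A reader might infer more than the documents support:

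- *SAP 3.4.2.1 is a second rule to record every AE to exit.* It sets outer limits only and is compatible with the 28-day windows.
- *The vaccine comparison is biased.* The written rule is the same for every group within a cohort, assessors are blinded and no formal comparison is planned.
- *The 86% and 92% are events missed.* They are shares of calendar time.
- *The pre-dose listing would be empty.* All SAEs have their own reporting route in 6.3.1.2.12.

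**Conclusion.** The conflicts are in the current text. Section 6.3.1.2.11 disagrees with 6.3.1.2.8, endpoint 1b and footnote p on when recording stops, and with 6.3.1.2 and SAP 3.4.2.1 on pre-dose events.

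The consequence for the tables is conditional. It holds if the 28-day rule operates, as the endpoint and both schedules indicate, or if sites differ in practice; if every site followed 6.3.1.2.11, capture would be complete. Under the 28-day rule and on-schedule dosing, the six end-of-study unsolicited tables have full capture for about one seventh of follow-up in Cohort A and one thirteenth in Cohort B. They should not be read as incidence to end of study, nor compared between cohorts as such. The defect is confined to those tables and the pre-dose listing. It should be corrected, but it does not threaten the primary safety endpoints.

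**What to change.** **Protocol.** Reconcile 6.3.1.2.11 with 6.3.1.2.8 and footnote p of Appendices 1 and 2 on when recording of non-serious unsolicited AEs stops. Reconcile it with 6.3.1.2 on whether pre-dose events are recorded as AEs or as medical history.

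**SAP 4.6.2.** Keep the all-unsolicited tables for the 28-day windows. Limit the end-of-study versions to the event types followed throughout, whether serious or not: SAEs, MAAEs, AESIs, and AEs leading to discontinuation, withdrawal or death. Put any other AE starting after the 28-day window in listings only, including one linked to an unscheduled visit that is not an MAAE. The minimum alternative is to keep the tables and footnote each with the change in ascertainment after 28 days.

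**Cost.** A clarifying sentence or two in the protocol, SAP wording, and either fewer tables or one standard footnote. No new data are needed.
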